**INSTRUCTIONS**

This template is intended to help investigators prepare a protocol that includes all of the necessary information needed by the IRB to determine whether a study meets approval criteria. **Read the following instructions before proceeding:**

1. Use this protocol template for a PI initiated study that includes direct interactions with research subjects. Additional templates for other types of research protocols are available in the system Library.
2. If a section or question does not apply to your research study, type "Not Applicable" underneath.
3. Once completed, upload your protocol in the "Basic Information" screen in IRES IRB system.

## SECTION I: RESEARCH PLAN

1. **Statement of Purpose:** State the scientific aim(s) of the study, or the hypotheses to be tested.

The purpose of this study is to develop and evaluate an innovative behavioral HIV prevention videogame intervention to bolster motivation and provide skill-building opportunities to improve Black adolescent girls' ability to negotiate around risk including advocating for partner HIV/STI testing, increasing their knowledge and awareness of HIV/STIs, and for reducing sexual risk-taking behaviors (1.e. non-condom use). As a multiplayer videogame, the intervention will be developed and delivered as a social, multiplayer videogame, a compelling context for Black adolescent girls who constantly interact and seek counsel from their peers.

To this end, our Specific Aims, focusing on Black adolescent girls aged 14-18 years, are to:

1. Translate our culturally and socially-tailored card game *One Night Stan* to a multiplayer videogame using game design and content experts and focus group input from 30 Black adolescent girls.
  2. Conduct a pilot randomized controlled trial comparing the multiplayer videogame *InvestiDate* intervention vs. an attention/control non-health-related multiplayer videogame with 80 participants collecting assessment data at baseline, one, and four months to:
    - a. Determine the intervention's acceptability and feasibility by collecting quantitative and qualitative data on Black adolescent girls' satisfaction and gameplay experience of the intervention.
    - b. Determine the preliminary impact of the intervention on knowledge (information), intentions/attitudes (motivation), social norms, and behavioral skills as related to: i) HIV/STI testing and partner testing and ii) condom use, and iii) sexual risk behavior reduction, such as alcohol and drug use.
2. **Probable Duration of Project:** State the expected duration of the project, including all follow-up and data analysis activities.
 

2 years
  3. **Background:** Describe the background information that led to the plan for this project. Provide references to support the expectation of obtaining useful scientific data.

Black women are disproportionately affected by HIV. At current rates, 1 in 32 Black women will be diagnosed with HIV in her life span. Given that Black women are often diagnosed late in the disease process, it is believed that many Black women were, in fact, infected in adolescence. Black adolescent girls between the ages of 14 and 19 are more than twice as likely than White girls (44% vs. 19%,  $p = 0.001$ ) to be diagnosed with an STI ( $p = 0.001$ ). Alarming, STIs are associated with an increase in the risk for HIV acquisition up to two- to fivefold. Research suggests that inadequate knowledge about HIV and the role of high-risk behaviors may contribute to the high HIV rates among Black women. For this reason, an early intervention that focuses specifically on Black adolescent girls in high school and that is gender and culturally tailored may decrease their risk for HIV/STIs infection.

Studies of social and behavioral determinants of disease have increasingly focused on the role of peer group structures on individual outcomes. Interactions in peer groups offer opportunities for individuals to exchange and evaluate information, to learn social norms, to develop behavioral skills,

and to influence each other's attitudes and behaviors. These interactions have important effects on knowledge and attitudes about risk, social support for risk and behavioral skills for prevention, and risk or preventive behaviors per se. For instance, a community-based pilot study demonstrated a 72% increase in the number of individuals getting tested for HIV/STI when peers recruited others through their social network. Similarly, a recent study of at-risk Black and Hispanic young women and adolescent girls, aged 13 to 24, found that a female friendship network method of engaging them was successful with increasing HIV testing rates of 90%.

Ninety-seven percent of teens ages 12-17 play computer, web, portable, or console games, and 94% of girls play video games. Social videogames, or games played with others, are the most popular and most frequently played game genre. Both non-digital and digital games have a well-established role in education because simulated role-playing is a highly effective approach for situated learning. Active participation through simulated role-playing enables individuals to practice behavioral change in a safe and entertaining way. Role-playing is a powerful mechanism for influencing people's attitudes. Game interventions have demonstrated efficacy in increasing knowledge and affecting behaviors and psychological variables related to health promotion and disease management in areas ranging from depression to medication adherence. There is also compelling evidence that individuals who acquire new information, motivation, behavioral skills in a gaming environment are more likely to act in accordance with the new skills in real life. Multiplayer social games are often more slowly and deliberately paced than single player games. This may help to create a shared experience with at least one other player, thus allowing for conversations between players and the opportunity to influence attitudes, beliefs, and perceptions around serious topics.

Although effective HIV/STI prevention programs for Black adolescent girls currently exist, including Diffusion of Effective Behavioral Interventions (DEBIs), such as Sisters Informing Healing Living and Empowering (SIHLE), Choosing Life: Empowerment! Action! Results! (CLEAR), and Focus on Youth with Informed Parents and Children Together (FOY+ImPACT), challenges regarding implementation and fidelity have been a concern. Recent studies have cited several barriers to the implementation of HIV/STI prevention interventions, including access to adequately trained providers, staff turnover, resource constraints of agencies, fidelity of the interventions, and challenges of adapting an intervention from one population to another. In addition to consistent fidelity and limited demand on program resources, the proposed multiplayer videogame offers some new features that could augment those found in many HIV prevention interventions that target Black adolescent girls as it will: 1) be packaged in a self-contained "vehicle" that is easily accessible and widely available; 2) be interactive with opportunities for players to build and practice skills; 3) allow for Black adolescent girls to engage with others or on their own, increasing their exposure (or "dose") to the intervention; 4) build upon elements that have been identified as being crucial for successful HIV/STI prevention in this population; and 5) not require personnel cost or staff training. Furthermore, given that videogame play is widespread, a game for HIV/STI prevention will allow for greater dissemination of this intervention and potential expansion of this concept to other high-risk populations.

4. **Research Plan:** Summarize the study design and research procedures using non-technical language that can be readily understood by someone outside the discipline. **Be sure to distinguish between standard of care vs. research procedures when applicable, and include any flowcharts of visits specifying their individual times and lengths.** Describe the setting in which the research will take place.

The purpose of this study is to translate the card game prototype, *One Night Stan*, into a multiplayer videogame with a focus on empowering Black adolescent girls to assess their risk, improve communication skills, and develop self-efficacy throughout their sexual experiences. By doing so, this digital intervention may provide an opportunity to reduce HIV/STI disparities in Black adolescent girls. To differentiate between the card game and the multiplayer videogame intervention, the videogame intervention has been named *InvestiDate*.

The study will take place in two phases. In **Phase 1**, we will conduct four focus groups with five participants each (20 participants) with Black adolescent girls to understand their attitudes, perceptions, and knowledge around communication about HIV/STI testing and condom use with partners. We will conduct focus groups at our partner settings, which include private rooms that we can access. Alternatively, we may conduct focus group sessions through Yale's videoconferencing tool, Zoom. We will then develop an alpha version of the multiplayer videogame *InvestiDate*, from the prototype card game, *One Night Stan*, using formative research and focus group data. Once developed, we will then conduct playtesting with focus groups (two focus groups with five participants each) to develop the beta version of the game. In **Phase 2**, we will pilot test the game intervention with 80 Black adolescent girls (aged 14-18 years) at partner sites in New Haven, Connecticut. Alternatively, we may conduct gameplay sessions through Yale's videoconferencing tool, Zoom, if in person meetings are not possible. If conducted in person, gameplay sessions will take place in private rooms dedicated to the study. If conducted remotely, we will ensure participants have access to a private room and Zoom-capable equipment. Participants will be randomly assigned to *InvestiDate*, or a non-health related multiplayer videogame that will serve as an attention/time control condition. All participants will play their assigned videogame for 1-2 hours, on two instances separated by approximately a week for between 2 and 4 hours of gameplay total. They will be evaluated at baseline, one, and four months.

**Setting:** For **Phase 1 and Phase 2**, recruitment and enrollment will take place either in person with partner schools and organizations or remotely either in partnership with schools that have agreed to collaborate with us, or through study advertisements placed on social media. Given our ability to play the videogame and collect data remotely, we are seeking additional partnerships with schools nationwide and recruiting participants individually through social media, including Facebook and Instagram. For Phase 1 (focus groups), recruitment may also take place online through social media platforms, including Facebook and Instagram. Focus groups will take place online through Zoom where participants will be able to see and interact with each other.

Of note, the Principal Investigator, [name] will not be involved in any aspects of consenting participants or their parents, the randomization process, data collection or direct performance of data analysis procedures.

**Participants:** For **both phases**, participants must be Black heterosexual adolescent girls aged 14 to 18 and currently enrolled in high school. For **Phase 2**, participants must also: 1) be able to participate in web-based videogame (willing to sit for 60-minutes/session to play the game); 2) not have been tested for HIV in the past year; and, 3) be able to provide assent/parental/guardian consent.

**Phase 1: Conduct focus groups and playtesting with Black adolescent girls and develop *InvestiDate*** (30 participants): Focus group discussions with Black adolescent girls will inform the new version of the game by providing ideas for content and gameplay around HIV/STI testing, condom use, and sexual risk taking. We have used and refined this iterative process for current videogame projects. Data collected will be used to inform the development of the multiplayer videogame, *InvestiDate*. Example question for the focus groups include, “What are some red flags that teens your age look for when considering dating someone?”, “What are some green flags that teens your age look for when considering dating someone?”, “What might make it difficult for teens your age to get tested for HIV/STIs?”

The card game prototype *One Night Stan* will be adapted as a multiplayer videogame called *InvestiDate* and will focus on a slightly younger age group. To do this we use formative research, pilot data, and focus group input to create an updated Game Playbook, or intervention manual that will be used to guide the development and design of the game.

**Phase 2: Pilot test *InvestiDate* compared with a control condition:** Participants will be randomly assigned to play either *InvestiDate* (n=40), or the non-health related attention and time control condition multiplayer videogame (n=40). Participants will be assigned to either the intervention or the control condition using a stratified randomization procedure. Age for the participant and partner testing in the last 30 days will be included in the randomization algorithm. Participants will be randomized by group so that the same group of participants will always play together.

**Assessments:** We will assess a range of pre-intervention participant characteristics (demographic), process measures, and outcomes (see below in Table 1). All assessments are standardized validated instruments that will be collected in person, using a web-based clinical trial management system we have used with our other studies. Assessments will be collected online using Yale-secured Qualtrics survey collection software. Baseline assessments are designed to ensure that all participants meet eligibility criteria and that important predictor variables are assessed. We will conduct post-intervention assessments immediately after gameplay sessions are completed (one month) with follow-up assessments at four months following enrollment to allow an adequate time for accumulation of outcome events.

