**Table 1: Assessments**

Assessment	Base-line	Month 1	Month 4
Participant Demographics (i.e. gender, age, education)	X		
HIV/STI Testing Rates and Partner HIV/STI Testing Rates	X	X	X
Sexual Risk Behaviors—Self-reported measures of sexual intercourse with/without condoms 	X	X	X
Vulnerability to Risky Sexual Behaviors 	X	X	X
Risk Behaviors Associated with HIV/STIs - Youth Risk Behavior Survey 	X	X	X
HIV Knowledge (HIV-KQ)  (45 item true/false questionnaire)	X	X	X
STI Knowledge (STD-KQ)  (27-item true/false questionnaire)	X	X	X
Subjective Norms 	X	X	X
Intentions 	X	X	X
Attitudes—Multi-dimensional Condom Attitudes Scale (MCAS) 	X	X	X
Self-efficacy in sexual risk behaviors—Sexual Risk Behavior Beliefs and Self-efficacy (SRBBS) Scales 	X	X	X
Condom Self-Efficacy (CUSES)  (28-item Likert scale)	X	X	X
Sexual Communication 	X	X	X
*Satisfaction with game play/acceptability and feasibility (12-item Likert scale) 		X	

5. **Genetic Testing** N/A

6. **Subject Population:** Provide a detailed description of the types of human subjects who will be recruited into this study.

Adolescents ages 14-18 will be recruited into this study.

7. **Subject classification:** Check off all classifications of subjects that will be specifically recruited for enrollment in the research project. Will subjects who may require additional safeguards or other considerations be enrolled in the study? If so, identify the population of subjects requiring special safeguards and provide a justification for their involvement.

- |  |  |  |
|--|--|--|
|  Children   |  Healthy                |  Fetal material, placenta, or dead fetus |
|  Non-English Speaking  |  Prisoners                         |  Economically disadvantaged persons      |
|  Decisionally Impaired |  Employees                         |  Pregnant women and/or fetuses           |
|  Yale Students         |  Females of childbearing potential |  |

NOTE: Is this research proposal designed to enroll children who are wards of the state as potential subjects?

Yes  No

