This protocol presents minimal risks to the subjects and Unanticipated Problems Involving Risks to Subjects or Others (UPIRSOs), including adverse events, are not anticipated. In the unlikely event that such events occur, Reportable Adverse Events (which are events that are serious or life-threatening and unanticipated (or anticipated but occurring with a greater frequency than expected) and possibly, probably, or definitely related) or Unanticipated Problems Involving Risks to Subjects or Others that may require a temporary or permanent interruption of study activities will be reported immediately (if possible), followed by a written report within 5 calendar days of the Principal Investigator becoming aware of the event to the IRB via the RNI submission process in IRES IRB and any appropriate funding and regulatory agencies. The investigator will apprise fellow investigators and study personnel of all adverse events that occur during the conduct of this research project through regular study meetings and via email as they are reviewed by the principal investigator. We will use procedures to detect and respond to adverse events that ensure prompt discovery of any adverse events and to minimize their effects. There is adequate surveillance and protections to discover adverse events promptly and keep their effects minimal. Data and safety monitoring procedures in this study include collection and monitoring of paper-based questionnaires and an organizational structure of clearly defined tasks assigned to all research personnel involved in the conduct of this study. We will keep a thorough record of research activities and completion of scheduled assessments.

We have established a Data Safety and Monitoring Board (DSMB) composed of two experts, [name] and [name], in clinical trials in young teens and in statistical analysis of clinical trials to oversee the safety and data integrity of this study. DSMB will also review the progress of the study.

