**SECTION IV: PROTECTION OF RESEARCH SUBJECTS**

**Confidentiality & Security of Data:**

1. What protected health information (medical information along with the HIPAA identifiers) about subjects will be collected and used for the research? *Name, Address, Telephone Number, Email Address, reported HIV/STI testing status and test results, sexual activity status*
2. How will the research data be collected, recorded and stored? All data collected from the assessments will be entered directly into the secure web-based system, Yale Qualtrics, which is Yale's enterprise-wide data management system. Research staff will enter the data into the Yale Qualtrics system. To assess acceptability and feasibility, directly following completion of the intervention, we will collect quantitative and qualitative data on the intervention participants' experiences of the game intervention.
3. How will the digital data be stored?  CD  DVD  Flash Drive  Portable Hard Drive  Secured Server  
 Laptop Computer  Desktop Computer  Other
4. What methods and procedures will be used to safeguard the confidentiality and security of the identifiable study data and the storage media indicated above during and after the subject's participation in the study?

Data will be stored in Yale's secured online data collection system, Yale Qualtrics. Paper assessments will be kept in a locked filing cabinet in the PI's office.

All portable devices must contain encryption software, per University Policy 5100. If there is a technical reason a device cannot be encrypted please submit an exception request to the Information Security, Policy and Compliance Office by clicking on url <http://its.yale.edu/egrc> or email [[contact]](mailto:[contact])

5. What will be done with the data when the research is completed? Are there plans to destroy the identifiable data? If yes, describe how, by whom and when identifiers will be destroyed. If no, describe how the data and/or identifiers will be secured.

Data collected in the study will reside in our computerized database and electronic storage mechanisms. All data analyses will be performed under approved HIC protocols. Digital files of the focus groups will be destroyed at the end of the study.

6. If appropriate, has a Certificate of Confidentiality been obtained? A CoC automatically covers this study due to its NIH funding.

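### Aim 2a determines feasibility from satisfaction and gameplay-experience data, so the stated measure would hardly register poor session attendance or retention

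*Combined protocol and SAP*

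**What the plan says.** Section I, item 1 (Statement of Purpose) sets Aim 2a as the first objective of the pilot trial: "Determine the intervention's acceptability and feasibility by collecting quantitative and qualitative data on Black adolescent girls' satisfaction and gameplay experience of the intervention". Acceptability and feasibility are named together and given one data source.

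Table 1 supplies one quantitative instrument for both, the row "Satisfaction with game play/acceptability and feasibility (12-item Likert scale"), marked at Month 1 only. The Assessments paragraph in Section I, item 4 times that visit: "We will conduct post-intervention assessments immediately after gameplay sessions are completed (one month"). Section IV, item 2 repeats the purpose and timing and restricts the data to the intervention arm: "To assess acceptability and feasibility, directly following completion of the intervention, we will collect quantitative and qualitative data on the intervention participants' experiences".

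The Research Plan describes the thing to be delivered: gameplay "on two instances separated by approximately a week for between 2 and 4 hours of gameplay total". Girls are randomised by group, and groups stay fixed across sessions. The arms are InvestiDate (n=40) and "the non-health related attention and time control condition multiplayer videogame (n=40").

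The Data and Safety Monitoring Plan (Section I, item 12) adds: "We will keep a thorough record of research activities and completion of scheduled assessments". That sentence is not linked to Aim 2a.

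**The concern.** Feasibility here is largely a delivery question. Can fixed groups of 14–18-year-olds be assembled, in person or on Zoom, and brought back together about a week later, and do the girls stay to Month 4? The direct evidence is attendance at each session with the assigned group, and completion of the follow-up assessments. A rating of how much a girl enjoyed the game records neither.

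The timing adds a second problem. Data tied to completion of the intervention may under-represent girls who missed a session, and those girls bear most directly on whether the format works.

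Attendance and retention are also among the quantities that a pilot of this size can estimate usefully. The statistical text calls the efficacy analyses exploratory and says that the results will inform the sample size of a full trial. That calculation needs a retention figure as well as an effect size.

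**Working it through.** The plan states no feasibility figure or threshold, so there is none to reproduce. The check asks how far the planned measure would move as attendance falls.

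**Inputs from the protocol:** 40 girls randomised to InvestiDate; two sessions; one scale at Month 1.

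**Assumptions, since the documents give no values:** attendance at both sessions between 40% and 90%; about 90% of attenders satisfied; in steps 1 and 2, only girls who attended both sessions answer.

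**Formulas.** With k girls attending both sessions and s of them satisfied:
- share among those answering = s/k
- lower bound over all 40 = s/40 (every non-answerer dissatisfied)
- upper bound over all 40 = (s + 40 − k)/40 (every non-answerer satisfied)
- attendance = k/40, with a Wilson 95% CI

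**Step 1, one case.** k = 24, s = 22.
- Among those answering: 22/24 = 91.7%.
- Bounds over all 40: 22/40 = 55% to (22 + 16)/40 = 38/40 = 95%.
- Attendance: 24/40 = 60%. Wilson centre = (0.6 + 3.8416/80)/(1 + 3.8416/40) = 0.64802/1.09604 = 0.591. Half-width = 1.96 × √(0.6 × 0.4/40 + 3.8416/6400)/1.09604 = 0.145. The 95% CI is 44.6% to 73.7%.

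**Step 2, the range.**

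| Attend both (k) | Satisfied (s) | s/k | Bounds over all 40 | Attendance (95% CI) |
|---|---|---|---|---|
| 36 | 32 | 88.9% | 80–90% | 90% (77–96%) |
| 32 | 29 | 90.6% | 72.5–92.5% | 80% (65–90%) |
| 28 | 25 | 89.3% | 62.5–92.5% | 70% (55–82%) |
| 24 | 22 | 91.7% | 55–95% | 60% (45–74%) |
| 20 | 18 | 90.0% | 45–95% | 50% (35–65%) |
| 16 | 14 | 87.5% | 35–95% | 40% (26–55%) |

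The figure among those answering stays at 88–92% while attendance falls from 90% to 40%.

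**Step 3, if everyone answers.** Drop the assumption that only attenders respond. Suppose that all 40 answer, attendance is still 24/40, and 14 of the 16 non-attenders liked what they played but could not return. Satisfaction is (22 + 14)/40 = 36/40 = 90%, with attendance at 60%. A full response removes the selection problem, but the score still does not reveal attendance.

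**Step 4, what the alternative could show.** Retention over both arms, taking 64/80 = 80% as an example, has a Wilson 95% CI of 70–87%. All these intervals treat girls as independent. Because they play in groups, attendance is probably correlated within a group and the true intervals would be somewhat wider.

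**The case against.** The strongest reply is that nothing in the protocol makes the scale conditional on attending both sessions. Table 1 places it at Month 1 beside the outcome measures. Completion of the sessions can be read as a calendar point for a group. Section VI pays per assessment, not per session, and the statistical text sets an intention-to-treat sample. A reader might infer that girls who skip session 2 are not asked, that 22/24 is the figure the plan would produce, and that the decision on a full trial would then rest on completers only. The documents do not support any of these. Who is asked is left open, the 92% is conditional on an assumption, and no text makes the scale a go/no-go rule. Nor is 55% the true acceptability in the example; it is only the lower end of a 55–95% range.

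Second, the measure is not empty. Qualitative data on gameplay could reveal technical, privacy or group-play problems. The content of the 12 items cannot be seen, and the Table 1 row carries an asterisk whose note does not appear in the text. This stands as a reason to keep both sources, but neither is described as counting attendance or retention.

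Third, the Assessments paragraph mentions process measures, and the monitoring plan promises records of activities and assessment completion. However, the paragraph refers to Table 1, where this scale is the only such row. The records fall under safety monitoring and do not name session attendance. Some text just before the statistical section was not available, so a provision there cannot be excluded.

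**Conclusion.** The point holds in a limited form. Aim 2a, Table 1 and Section IV agree in determining feasibility, as well as acceptability, from satisfaction and gameplay experience collected once after the gameplay sessions. No available text uses attendance or retention for that aim. The stated method therefore answers the feasibility part of the aim poorly.

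The size is illustrative only. If just the attenders answer and about 90% of them are satisfied, the result is nearly unchanged over attendance from 90% to 40%. Under-representation of girls who miss a session is a possibility left open by the wording. The main conclusion does not depend on it, because even a fully answered scale does not report attendance. The correction is a cheap improvement and leaves the trial's design unchanged.

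**What to change.** In Aim 2a and Section IV, item 2, determine feasibility from two sets of proportions over all randomised girls: attendance at session 1 and at session 2 with the assigned group, and completion of the Month 1 and Month 4 assessments. Report each by arm with a 95% CI, preferably allowing for play group. Use the activity and assessment-completion records promised in the Data and Safety Monitoring Plan, and add a session attendance log if those records do not already capture it.

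Keep the 12-item scale and the qualitative data for acceptability and gameplay experience. State that the Month 1 scale goes to every girl due to receive it, regardless of sessions attended. Report it with the number not answering and broken down by sessions attended.

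This alone sets no criterion for calling the game feasible. It makes attendance visible, and any threshold would be for the investigators to state in advance.

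The cost is rewording in two places, one table and possibly a simple log, with no extra participants, visits or instruments. The downside is that the reported acceptability and feasibility figures may be less favourable.

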HIV/STI testing and partner testing in comparison to the control condition. We will conduct a longitudinal analysis using a hierarchical linear mixed models approach to compare participants in the intervention group to participants in the control group on reported participant and partner HIV/STI testing from baseline across all follow-up assessments (i.e., baseline, one month and four months). Hierarchical modeling will allow us to account for the fact that the data are nested as the participants will play the game in groups. An advantage of mixed models is that participants with missing data need not be excluded as all available data are used in estimating parameters. We will also use logistic regression models to determine if any relevant baseline variables are associated with improvement in reported HIV/STI testing or partner testing (constructed as a binary outcome (Yes/No)). We plan to evaluate the prognostic significance of a small set of predictor variables (e.g., intentions, attitudes, self-efficacy, social norms, and knowledge) and use them as covariates in the primary analysis. All of these analyses will be exploratory given the study sample size.

SECTION II: RESEARCH INVOLVING DRUGS, BIOLOGICS, RADIOTRACERS, PLACEBOS AND DEVICES
--

- |                    |   |
|--------------------|---|
| A. RADIOTRACERS    |  N/A |
| B. DRUGS/BIOLOGICS |  N/A |
| C. DEVICES         |  N/A |

SECTION III: RECRUITMENT/CONSENT AND ASSENT PROCEDURES
---

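### Age and recent partner testing enter the randomisation, but the primary model is not committed to either; naming both as covariates is a small, nearly free improvement

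*Combined protocol and SAP*

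**What the plan says.** **Randomisation (Section I, Phase 2).** Eighty girls are allocated, 40 per arm: "Participants will be assigned to either the intervention or the control condition using a stratified randomization procedure". The factors follow: "Age for the participant and partner testing in the last 30 days will be included in the randomization algorithm". The next sentence adds: "Participants will be randomized by group so that the same group of participants will always play together". No strata cut-points or play-group size are given.

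**Baseline data (Table 1).** Age is collected at baseline under "Participant Demographics (i.e. gender, age, education". Testing is collected at all three visits under "HIV/STI Testing Rates and Partner HIV/STI Testing Rates", with no recall window stated.

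**Analysis (Section I, Data Analyses General Considerations and the text that follows).** A longitudinal mixed model compares the arms on the girl's own and her partner's testing over baseline, month 1 and month 4. A hierarchical structure is used because "the data are nested as the participants will play the game in groups". Covariates are tied to an assessment of how prognostic a few baseline measures are, described in these words: "predictor variables (e.g., intentions, attitudes, self-efficacy, social norms, and knowledge) and use them as covariates in the primary analysis". Testing is also treated as a yes/no outcome in logistic models that look for baseline predictors. The plan expects low power for small effects, labels the analyses exploratory, and intends the results to support the sample size of a full-scale trial.

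**The concern.** Factors used to balance the arms normally belong in the primary model, whatever association they show in the data. If they predict the outcome and are left out, the linear-model standard error still counts variation that the design has already balanced between the arms. It is then too large, and precision is lost. Here the model's covariates come through a prognostic assessment, and the examples are all psychosocial scales. An analyst could follow the text to the letter and fit a model without age or prior partner testing.

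The gap is widest for age, which appears nowhere in the model text. Partner testing is partly covered when it is itself the outcome, because its baseline value is one of the model's time points. It is not covered when the girl's own testing is the outcome. Precision matters even in a pilot whose effect sizes are meant to inform the next trial.

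**Working it through.** The documents give no power or precision figure to reproduce. The one arithmetic check is 40 + 40 = 80, which agrees with the stated sample.

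**Inputs.** From the documents: 80 girls, 1:1 allocation, three visits, a play-group effect in the model. Assumed, because the documents are silent: play groups of m = 4, group ICC 0.05, outcome variance 1, within-girl correlation r between visits of 0.3, 0.5 or 0.7, complete data, a continuous outcome, and balanced factors that together explain R² = 0.05, 0.10 or 0.20 of the variance with the same effect at each visit.

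Write A = 1 + (m − 1) × ICC = 1 + 3 × 0.05 = 1.15 for the variance including clustering, and c = r + 0.15 for the matching covariance between baseline and month 4. Adjusting for the factors lowers both A and c by R².

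**Case 1: plain arm-by-time contrast (change from baseline to month 4).** The variance is proportional to 2(A − c) = 2(1 − r). After adjustment it is 2[(A − R²) − (c − R²)] = 2(1 − r), the same. The ratio of unadjusted to adjusted SE is 1.000 in all nine settings, because time-invariant covariates cancel.

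**Case 2: baseline means constrained equal.** The variance is proportional to A − c²/A = (A − c)(A + c)/A. As A − c does not change with adjustment,

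SE ratio = √{ [(A + c)/A] ÷ [(A + c − 2R²)/(A − R²)] }.

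For r = 0.3 and R² = 0.20: A + c = 1.15 + 0.45 = 1.60, so the ratio is √{(1.60/1.15) ÷ (1.20/0.95)} = √1.1014 = 1.0495.

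**Case 3: baseline uninformative (month-4 levels only).** SE ratio = √[A/(A − R²)]. For R² = 0.20 this is √(1.15/0.95) = 1.100.

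Increase in SE from leaving the factors out:

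| R² | Case 1 | Case 2, r = 0.3 | Case 2, r = 0.5 | Case 2, r = 0.7 | Case 3 |
|---|---|---|---|---|---|
| 0.05 | 0% | 1.01% | 0.64% | 0.34% | 2.25% |
| 0.10 | 0% | 2.15% | 1.35% | 0.72% | 4.65% |
| 0.20 | 0% | 4.95% | 3.06% | 1.62% | 10.02% |

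**Which case applies.** The plan does not say how the arm effect is parameterised. The eligibility criteria exclude girls tested for HIV in the past year, so baseline carries little information on own HIV testing, and an analysis of follow-up levels of that outcome is close to Case 3. STI testing is not excluded in this way, and partner testing can vary at baseline, so Cases 1 and 2 are more relevant there.

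**Simulation check of Case 3** (3000 runs per setting, one continuous follow-up, random intercept for group, girls stratified and then grouped within arm). Model SE without and with the factors, groups of 4: 0.244/0.239, 0.243/0.232 and 0.242/0.219 at R² = 0.05, 0.10 and 0.20. These are ratios of 1.02, 1.05 and 1.11, in line with the formula. Over groups of 4 and 5 and both ways of applying the factors (to girls or to groups), type I error at R² = 0.10 and 0.20 was 2.4-3.4% and 2.1-2.4% unadjusted, against 3.4-4.0% and 3.8-4.1% adjusted. The unadjusted test is therefore conservative. With R² = 0, adjusting cost at most 1 point of power for an assumed 0.6 SD effect.

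**The case against.** - **The covariate list is only illustrative.** It opens with an example marker, so a reader who infers that the plan excludes the randomisation factors goes further than the text. This stands. The point is lack of commitment, not contradiction.
- **The planned model is longitudinal, so the 10% figure does not describe it in general.** This stands and governs the size. Adding two time-invariant covariates to a plain arm-by-time model changes nothing on complete data. The 2, 5 and 10% figures apply only where baseline says little about follow-up.
- **Testing is a yes/no outcome.** This also stands. In logistic regression, adjustment need not shrink the standard error of the log odds ratio, so the figures above are linear-model results.
- **The trial is an exploratory pilot and the error is conservative.** Agreed, and this keeps the severity low. It does not remove the case for a change that needs a sentence or two.

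A reader might also infer that randomising by group makes the stratification unworkable, since a mixed group has no single stratum. The documents do not support that. The allocation sentences take participants as the unit, and the stated purpose of grouping is that the same girls keep playing together. Stratifying girls and then fixing groups within arm is a coherent reading. Nor do the documents support an inference that the arms may drift apart on these factors, because the plan says that both are in the algorithm.

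**Conclusion.** The point holds as an under-specification with a nearly free remedy. The trial balances on age and recent partner testing, and the available analysis text does not commit the primary model to either. For a linear model the omission does not bias the effect estimate or inflate false positives. It costs precision: about 0-5% of the standard error where the baseline outcome is informative, and about 2, 5 or 10% where it is not, if the factors explain 5, 10 or 20% of variance. Play-group size, ICC, within-girl correlation and variance explained are all assumed, and the figures are for a continuous outcome with complete data. Severity is minor. The unit of allocation needs a clarifying sentence and is not a defect in its own right.

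**What to change.** In the analysis section:
- Enter age and baseline partner testing, using the value fed to the randomisation algorithm, as fixed covariates whatever their observed significance.
- Keep the play-group random effect.
- Estimate the follow-up arm difference with baseline means constrained equal across arms, or with the baseline outcome as a covariate. Without this, the added covariates do nothing for the month-4 contrast.
- Where partner testing is the outcome, let its baseline measurement serve for that factor, provided it uses the same 30-day window. Table 1 does not state the window, so state it.

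In the randomisation paragraph, as a clarification only, say whether girls are stratified and then placed in fixed groups within arm, or whole groups are allocated.

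**Cost.** A few sentences. No new data are needed if the 30-day value used for randomisation is retained. The model gains two terms with n = 80, which costs about 1 point of power at most if the factors turn out not to be prognostic.
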